Based upon published reports, we anticipate that participants in the intervention arm of the study will experience a health benefit; they will be less likely to acquire TD while abroad. They also may benefit, in the event that they do acquire TD, by having a shorter duration and lesser severity of TD symptoms in comparison to those in the placebo group.

Description of the Potential Risks to Anticipated Benefit Ratio

The potential benefits of participating in this study outweigh the minimal risks.

Emergency Care

We do not anticipate participants needing emergency care as a part of this study.

Participants will be provided phone and email contact information for study personnel in the event questions or concerns arise that may relate to their participation in the study.

Study Timeline

Table 1. Study Timeline, 2017–2020

Study Component	Date of Anticipated Start	Date of Anticipated End
Protocol Writing and Coordination	March 2017	October 2017
Submission of protocol/consent forms for IRB approval	November 2017	Late December 2017
Training of study personnel	January 2018	January 2018
Enrollment of participants	February 2018	July 2019
Laboratory analysis of stool specimens	February 2018	October 2019
Data entry	February 2018	October 2019
Data analysis (every 3 months)	April 2018	November 2019
Manuscript writing and clearance	November 2019	March 2020
Dissemination of findings	March 2020	

Study Population

Description and Source of the Study Population

Participants will be selected from persons seeking a pre-travel consultation at The New York Center for Travel and Tropical Medicine, New York, United States. This clinic serves travelers by providing pre-travel consultative services, in addition to post-travel screening, assessment, diagnostic, and treatment services. Centrally located in Manhattan, this clinic serves a large variety of international travelers, including tourists, immigrants or their relatives, and business travelers, among others. Travelers' destinations are equally varied, reflecting the ethnic and cultural diversity of New York City.

Definitions

Diarrhea:

≥ 3 unformed stools in 24 hours, with or without associated symptoms such as fever, cramping, or abdominal pain

Travelers' diarrhea:

Diarrhea that begins while traveling (after arrival in a country) or within 10 days after return

Study period:

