9. Have had diarrhea (see Definitions) anytime in the previous 30 days, have diarrhea at the pre-travel consultation, or develop diarrhea before departure
10. Have been given doxycycline for malaria prophylaxis for the current trip (due to possible drug-drug interactions and decreased absorption of the doxycycline) (27)
11. Have an allergy to any component of the placebo tablets

Estimated Number of Participants

We anticipate enrolling approximately 500 participants (see Sample Size and Power Calculation).

Sample Size and Power Calculation

A sample size of 488 participants with full compliance to medications and questionnaires (244 participants in each arm) is needed to fulfill the objectives [anticipated incidence of the endpoint as 40% incidence of TD with a 30% minimum intervention protection ($0.40-[0.4 \times 0.30] = 0.28$) with an alpha of 0.05, and 80% power].

Recruitment and Enrollment

All international travelers undergo a screening questionnaire at their pre-travel consultation to determine eligibility. This short questionnaire includes questions regarding the travelers' [see **APPENDIX A**]:

1. Age
2. Travel destination(s)
3. Trip duration
4. Acute and chronic medical conditions, including diarrhea
5. Contraindications to BSS administration
6. All current medications, including antibiotic use within the 30 days before screening
7. Willingness to participate in the trial and comply with the data collection requirements

This screening questionnaire will be administered to the traveler by study personnel at The New York Center for Travel and Tropical Medicine. The purpose will be to exclude those travelers who do not meet all inclusion criteria and those who meet any exclusion criteria (see Participant Inclusion / Exclusion Criteria). Travelers who meet the inclusion criteria and do not meet any exclusion criteria will be introduced to the project objectives and procedures, including the procedures for biologic (stool) specimen collection (see Laboratory instruments).

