Dosing will begin on the flight prior to arrival in the destination and will cease once they return home. The study medications must be taken twice daily (a morning and an evening dose); with time zone changes, the first dose should be taken to ensure that no longer than 12 hours passes before a subsequent dose.

Before departure, participants will be provided, free of charge, all needed study medication for the duration of their trip. Participants will be encouraged to take all doses of their medication and appropriately document on their daily during travel questionnaires if a dose was missed or taken off schedule.

Outcomes

The outcomes of this study will include:

	Favorable Outcome	Non-favorable Outcome
Hypothesis 1: Prevention of TD	Prevention of TD in the intervention group	TD in the intervention group at a rate similar to placebo; intervention drug side effects; adverse events

Hypothesis 2: Acquisition of AMR genes	Reduced or no presence of travel-associated gut AMR genes in the intervention group	No reduction in the presence of travel-associated gut AMR genes in the intervention group
---	---	---

The participant's study period will end in the following circumstances:

1. The traveler meets criteria for removal (see Criteria for Removal from the Study)
2. The participant voluntarily withdraws from the study (see Procedures for Implementing and Documenting Informed Consent)
3. The participant completes all study activities and submits all study questionnaires and biologic (stool) specimens
4. The participant is lost to follow-up

The participants will be instructed at enrollment to stop the study medication for any of the following reasons (although they will still be instructed to answer their questionnaires and submit biologic [stool] specimens as scheduled):

1. Antibiotics or BSS (either provided by the study personnel for TD treatment, or taken as an over-the-counter remedy) are taken for TD or for another medical condition
2. Any severe adverse events as described, such as signs and symptoms of salicylism or neurotoxicity, occur
3. Hospitalization for any reason

Barring the reasons listed above, the study medication should be taken throughout the trip duration, even if diarrhea occurs, if possible.

Criteria for Removal from the Study

Participants will be removed from the study when any of the following criteria apply:

1. Do not complete the pre-travel questionnaire (see Definitions for compliance)
2. Loss to follow-up (see Definitions)

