- Chemotherapeutic agents (e.g., including methotrexate [Trexall])
- Tumor necrosis factor (TNF) blockers (e.g., etanercept [Enbrel], adalimumab [Humira], certolizumabpegol [Entyvio], golimumab [Simponi], and infliximab [Remicade])
- Monoclonal antibodies (e.g., rituximab [Rituxan] or alemtuzumab [Lemtrada])
- Insulin (e.g., Humalog, NPH, Lantus, Levemir)
- Valproic acid (e.g., divalproex, Depakote, Depacon)
- ACE-inhibitors (e.g., lisinopril [Zestril], enalapril [Vasotec], captopril [Capoten], ramipril [Altase], benazepril [Lotensin])
- Anticoagulants (e.g., warfarin [Coumadin], aspirin, clopidogrel [Plavix], argatroban [Acova], bivalirudin [Angiomax], dabigatran [Pradaxa])

Yes

No*

Don't know

11. Do you have any of the following chronic stomach or intestinal illnesses?

- Irritable bowel syndrome (IBS)
- Inflammatory bowel disease (including ulcerative colitis and Crohn's disease)
- Celiac disease; any form of chronic diarrhea or chronic abdominal pain;
- Pancreatic insufficiency
- Gallbladder disease
- Malabsorption syndromes
- Gastrointestinal malignancy/cancer currently receiving chemo; radio, or immunotherapy
- Chronic diarrhea from another cause

Yes No* Don't know**12. Do you have any illnesses that you have been told lowers your body's ability to fight infection?**

- Missing or non-functioning spleen
- Insulin-dependent diabetes mellitus
- Diabetes mellitus receiving oral hypoglycemic medications (e.g. metformin, glyburide)
- HIV/AIDS
- Other immunodeficiency syndrome (e.g. complement deficiency, antibody or immunoglobulin deficiency)
- Malignancy or cancer under active chemo, radio, or immunotherapy; or any other immunocompromising condition?

 Yes No* Don't know**13. Have you ever received a solid organ transplant?** Yes No* Don't know**14. Have you had diarrhea (3 or more unformed stools in 24 hours) in the 30 days before enrollment or do you currently have diarrhea?** Yes No* Don't know

*Must answer "Yes" to questions 1, 2, 3, AND 4 and "No" to all subsequent to be eligible for enrollment.

 Eligible per Appx A Not Eligible per Appx A

Comments:

By signing below, I confirm that I conducted the verbal screening and have reviewed the answers before proceeding with additional study activities:

Name of Interviewer		Signature	
Date			

If eligible, collect the following:

Participant First Name: _____ Participant Last Name: _____

State of Residence: _____ County of Residence: _____

Residence Zip Code: _____

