APPENDIX D: During-travel Questionnaire

During Travel Questionnaire

PARTICIPANT UNIQUE ID: _____

GROUP ID: _____

	Day 1	Day 2	Day 3	Day 4	Day 5
Please write the calendar date that corresponds to each day of your trip. Day 1 is your first day of arrival in the country.					
Number of tablets taken in the morning (maximum 4)					
Number of tablets taken in the afternoon/evening (maximum 4)					
Symptoms in the prior 24 hours (check off all that apply)	... 				
Fever					
Nausea					
Vomiting					
Loose stools (less than three in a 24 hour period)					
Diarrhea (three or more loose stools in 24 hours)					
Bloody diarrhea					
Constipation					
Dark or black stool					
Dark or black tongue					
Abdominal pain					
Abdominal cramps					
Urgency to relieve oneself (in reference to stool)					
Bloating					
Flatulence/gas					
Congestion/runny nose					
Sore throat					
Cough					
Rash					
Headache					
Dizziness					
Ringing in your ears					
Muscle pain/soreness					
Joint pain/swelling/redness					

Drowsiness (severe)					
Confusion					
Depression					
Other (list/describe):					
Medical care
Did you seek medical care for one or more of these symptoms? (Yes/No/Don't Know)	Y N D	Y N D	Y N D	Y N D	Y N D
→ If yes, where? (check the corresponding box(es))
A doctor's office					
Urgent care clinic (outpatient)					
Emergency room					
Hospital outpatient clinic setting					
Hospital inpatient ward – hospitalized					
Other (specify)					
→ Was your diagnosis travelers' diarrhea? (Yes/No/Don't Know)	Y N D	Y N D	Y N D	Y N D	Y N D
Have you started any medications in the past 24 hours? (Yes/No/Don't Know)	Y N D	Y N D	Y N D	Y N D	Y N D
→ If yes, what medication(s)?					
→ Please circle those that were provided for you at your pre-travel consultation with the study clinic.

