What city(ies) and country(ies) have you been in during the past 24 hours? Please write answers to all questions in the corresponding box.					
Have you eaten any of the following in the past 24 hours? (Yes/No/Don't Know)
→ Fermented or pickled foods (e.g., bean paste, fish kimchi, etc.)	Y N D	Y N D	Y N D	Y N D	Y N D
→ Yogurt	Y N D	Y N D	Y N D	Y N D	Y N D
Did you have any diarrhea between completing the pre-travel questionnaire and arriving in the country? (Yes/No/Don't Know)	Y N D
Comments:					

PARTICIPANT UNIQUE ID: _____

GROUP ID: _____

	Day 6	Day 7	Day 8	Day 9	Day 10
Please write the calendar date that corresponds to each day of your trip. Day 1 is your first day of arrival in the country.					
Number of tablets taken in the morning (maximum 4)					
Number of tablets taken in the afternoon/evening (maximum 4)					
Symptoms in the prior 24 hours (check off all that apply)
Fever					
Nausea					
Vomiting					
Loose stools (less than three in a 24 hour period)					
Diarrhea (three or more loose stools in 24 hours)					
Bloody diarrhea					
Constipation					
Dark or black stool					
Dark or black tongue					
Abdominal pain					
Abdominal cramps					
Urgency to relieve oneself (in reference to stool)					
Bloating					
Flatulence/gas					
Congestion/runny nose					
Sore throat					
Cough					
Rash					
Headache					
Dizziness					
Ringing in your ears					
Muscle pain/soreness					
Joint pain/swelling/redness					
Drowsiness (severe)					
Confusion					
Depression					

Other (list/describe):					
Medical care
Did you seek medical care for one or more of these symptoms? (Yes/No/Don't Know)	Y N D	Y N D	Y N D	Y N D	Y N D
→ If yes, where? (check the corresponding box(es))
A doctor's office					
Urgent care clinic (outpatient)					
Emergency room					
Hospital outpatient clinic setting					

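### The arrival-day diary entry and its one undated question on earlier diarrhea cannot show whether Day 1 diarrhea began before or after arrival, and no rule says how to score it

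*Combined protocol and SAP*

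**What the plan says.** **Endpoint.** The Definitions section of the protocol defines TD as "Diarrhea that begins while traveling (after arrival in a country) or within 10 days after return". Whether an episode is a primary endpoint event therefore depends on when it began.

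**Diary.** In Appendix D the column headings explain that "Day 1 is your first day of arrival in the country". The symptom block is headed "Symptoms in the prior 24 hours (check off all that apply"), in the same words for every day, Day 1 included. The grid has no onset date or time.

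**Bridging question.** The first diary page also asks, once and under Day 1 only: "Did you have any diarrhea between completing the pre-travel questionnaire and arriving in the country". The answer is Yes, No or Don't Know.

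**Eligibility.** Participant Exclusion Criteria, item 9, has three limbs: "Have had diarrhea (see Definitions) anytime in the previous 30 days, have diarrhea at the pre-travel consultation, or develop diarrhea before departure".

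**Dosing.** The Intervention section says: "Dosing will begin on the flight prior to arrival in the destination and will cease once they return home". A participant in transit may therefore already have taken study medication.

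**The concern.** The bridging question covers two periods with different consequences. Diarrhea between the pre-travel questionnaire and departure bears on eligibility. Diarrhea between departure and arrival does not, and it is not TD either. One undated answer cannot tell them apart, and it does not say whether the diarrhea had stopped by arrival.

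A participant who answers Yes or Don't Know and ticks diarrhea on Day 1 could have had onset before departure, in transit or after arrival. If the tick is taken at face value, episodes outside the plan's own definition enter the primary endpoint. If these participants are set aside instead, some true TD cases and some eligible participants are lost. With no rule, the choice is made after the data are in, and later analysis cannot recover an onset time that was never recorded. A Yes also cannot confirm or rule out the third limb of exclusion 9.

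**Working it through.** **1. Does another part of the plan supply the onset time?**

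- Study Instruments, During Travel, lists duration of GI symptoms among the daily data, but the Appendix D form has no duration field.
- The post-travel questionnaire (Appendix E) asks about symptoms since returning home. Its recall list for the travel period does not include diarrhea.
- Quality Control and Assurance says data are entered as received and not altered. It describes no query step for an ambiguous entry.
- Appendix I, Table 2 (the TD table shell) gives no derivation of TD.

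None of these resolves the case.

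**2. Which answers are ambiguous?**

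| Bridging question | Day 1 diarrhea ticked | Can onset be placed? |
|---|---|---|
| No | Yes | Yes: after arrival |
| Yes or Don't Know | Yes | No |
| Yes or Don't Know | No, first tick on Day 2 | Ordinarily yes: after arrival |

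Only the middle row is a problem for the endpoint. Separately, any Yes is uninformative about the before-departure limb of exclusion 9.

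**3. How long is the uncovered interval?** The pre-travel questionnaire is completed by phone from 7 days before departure (Study Instruments, Pre-travel). Later calls, on days 5, 3 and 1, are made only as needed to get it completed. Up to about a week plus transit can therefore rest on self-report and the bridging question.

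**4. The plan's sample size.** Inputs from Sample Size and Power Calculation: 40% TD on placebo, 30% protection, so 0.40 − 0.40 × 0.30 = 0.28 on BSS; alpha 0.05 (sidedness not stated; two-sided used here); 80% power. The pooled-variance formula without continuity correction, with p̄ = 0.34, is

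n = [1.960 × √(2 × 0.34 × 0.66) + 0.842 × √(0.40 × 0.60 + 0.28 × 0.72)]² / 0.12² = 243.4, which rounds up to 244 per arm.

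This reproduces the stated 488. Power at 244 per arm is 80.1%.

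**5. Effect if pre-arrival cases are scored as TD.** The documents give no rate. Let f be the share in each arm with pre-arrival diarrhea that is scored as TD, assumed equal in both arms. The observed rates become

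placebo = 0.40 + 0.60f; BSS = 0.28 + 0.72f; protection = 1 − BSS/placebo.

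| f (assumed) | Placebo | BSS | Protection | Power at 244 per arm | Total N for 80% |
|---|---|---|---|---|---|
| 0 | 40.0% | 28.0% | 30.0% | 80.1% | 488 |
| 0.5% | 40.3% | 28.4% | 29.6% | 79.5% | 496 |
| 1% | 40.6% | 28.7% | 29.3% | 78.9% | 502 |
| 2% | 41.2% | 29.4% | 28.5% | 77.7% | 518 |
| 5% | 43.0% | 31.6% | 26.5% | 74.2% | 564 |

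**6. Effect if they are dropped instead.** Losing 1% or 2% of each arm at 40% vs 28% leaves power at 79.7% or 79.3%.

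**7. Is 1–2% a reasonable scale?** As a rough comparison, assume a constant hazard. A 40% risk over 7 to 21 travel days plus 10 days after return (17 to 31 days) gives −ln(0.60)/31 = 1.6% to −ln(0.60)/17 = 3.0% per day. An f of 5% from about one pre-arrival day would exceed even that average rate. Episodes persisting from earlier could add to it.

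**The case against.** **Exclusion 9 is applied elsewhere.** A reader might infer that exclusion 9 cannot be applied, or that the bridging question is the only check on diarrhea before arrival. The documents do not support either reading. Screening item 14 asks "Have you had diarrhea (3 or more unformed stools in 24 hours) in the 30 days before enrollment or do you currently have diarrhea". Staff review every screening answer by phone before departure (Study Instruments, Pre-travel; Appendix G). Under Recruitment and Enrollment, participants also agree to report diarrhea before departure so that eligibility can be judged again. What remains is narrower: a Yes on the diary cannot verify the last limb. Nor do the Criteria for Removal list diarrhea before departure, so only the co-principal investigators' discretion could cover it.

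**The bridging question already flags the doubtful cases.** This is largely right. A No supports onset after arrival, and a Yes marks the cases that may fail the definition. Nothing says analysts would ignore it, so the figures in step 5 describe the case where every flagged episode is still counted. But flagging a case does not place its onset, and no rule says what to do with it.

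**The look-back may be short.** Each column has morning and evening tablet rows, which suggests completion at the end of the day. The overlap with pre-arrival time may often be only partial. The form fixes no entry time, so some overlap remains possible.

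**The bias need not be equal across arms.** A reader might also infer that study drug could not have prevented any of these episodes. That does not hold for all of them: dosing starts on the flight, and Current State of Knowledge reports bacterial inhibition in as little as 0.5 to 24 hours. Equal misclassification is an assumption, most plausible for onset before departure.

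**Conclusion.** The point holds in a limited form. The definition of TD depends on onset after arrival. For one pattern of answers, Yes or Don't Know with diarrhea ticked on Day 1, the form cannot show onset and the plan has no scoring rule. Such cases can be counted as TD against the plan's own definition.

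This is a minor point. On the working assumption that 1–2% of each arm (5 to 10 of about 500 participants) is affected, equally by arm and all scored as TD, protection falls by 0.7 to 1.5 percentage points and power by 1.2 to 2.4 points. Under those assumptions the bias is toward no effect. The sample size itself is correct as calculated. The reason to act is that the missing information cannot be collected later and is almost free to collect now.

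**What to change.** - Split the bridging question in two: (a) diarrhea after the pre-travel questionnaire and before departure, with the last date; (b) diarrhea between departure and arrival, and whether it was still present on arrival.
- In the Day 1 column, record whether any ticked diarrhea began before or after arrival.
- Add one endpoint-derivation sentence, fixed before unblinding: an episode with onset before arrival is not TD, and a separate new episode that starts after arrival is.
- State how randomized participants who answer Yes to (a) are handled in the analysis.

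Recording onset directly is safer than only rewording the Day 1 heading to cover symptoms since arrival. A late arrival would leave just a few hours against a 24-hour stool count, and ongoing earlier diarrhea could still be ticked.

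The cost is one or two extra questions on a single day, a small form revision with the IRB amendment that the protocol requires for instrument changes, and two sentences in the analysis plan.
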